# Secondary end-points are:

- Composite number of adverse events such as new-onset sepsis, toxic megacolon, positive post FBT blood culture, or other SAE assessed by the physician-in-charge as possibly related to FBT.
- SOFA score at days 4 and 7.
- Percentage of patients that are recurrence-free at time of hospital discharge or day 28, whichever occur earlier.
- Subgroup analysis will be performed for patients who are C. dif. positive vs. negative and those who will receive antibiotics for a new extraabdominal infection vs. those who do not.

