#### Sample study size:

We plan to randomise 36 patients in 1:1 ratio: This is a pilot trial, with primary outcome being feasibility and safety of faecal bacterial transplantation in the population of critically ill adults with C. dif. positivity and diarrhoea. However, with 36 randomised patients, the study will have sufficient power to determine non-inferiority against standard-of-care based on data available in FBT in patients with C. dif. In two trials in non-critically ill patients, the success of FBT was 69% (22 out of 32) or 56% (5 out of 9) as compared to 45% cured by oral metronidazole. Assuming that clinically significant difference between the two methods is 20% and the intervention will be as effective in ICU patients as it was in the non-critically ill group (curing 27 out of 41, ie. 66%), if there is a true difference in favour of the experimental treatment of 21%, then 36 patients are required to be 80% sure that the upper limit of a one-sided 95% confidence interval (or equivalently a 90% two-sided confidence interval) will exclude a difference in favour of the standard group of more than 20%. The expected duration of participation in the study is 6 months.

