# Intervention group :

- if considered safe, the patient receive Loperamide 2 mg p.o. 2 hours before FBT.
- FBT procedure 350 ml of thawed donor stool (stool suspension) will be delivered by retention enema in the patients colon. The patient will be positioned in left semilateral Trendelenburg's position for 15 minutes and then in right semilateral Trendelenburg's position for another 15 minutes. Faecal management system (e.g. FlexiSeal©) will be inserted and clamped for 2hours after FBT
- in all patients receiving FBT will be recorded body temperature, heart rate, oxygen saturation and blood pressure. 3hours after FBT blood culture will be taken.

- in the subset of patients with C. dif. positivity, 1 L normal saline enema will be performed at the time of CDI diagnosis and FBT will be repeated once more. No antibiotics will be administered (with rescue option of administration of i.v. tigecycline).

**FBT stool suspension** will be stored in specific –80°C freezer with connected alarm notification to guarantee continuous registration of the storage. Information on the FBT suspension labels includes donor code, suspension number, production and expiration date, volume, and storage temperature instruction. From each donor one of the sample will be store in freezer for the duration of the ongoing study.

The resulting faecal bacteriotherapy (FBT) preparation is defined as a mixture of 7 aliquots of processed stool intermediates from 7 donors.

The resulting graft will be drawn into four sterile 100 ml syringes and transferred to the ward where the recipient is hospitalized. Re-freezing of thawed or partially thawed extract is not permitted.

# Day 2, 3

Physical examination, SOFA score, evaluation of laboratory blood results (WBC, CRP, lactate, etc.) will be recorded as well as volume or frequency and consistency (Bristol scale) of stool. Concomitant medication and adverse events will be recorded.

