# Assessment of primary outcome:

An independent data analyst will retrospectively review the de-identified printouts of nursing notes from the two 12 hour shift day + night ending in the morning of day 7 and record the presence or absence of diarrhoea (defined as 3 or more stools per day or Bristol type 7 stool in the volume >300 ml/day if stool derivative device is inserted).

In case the patient is not on ICU, but remains at hospital, the research nurse will bring a special record form on day 6 and instruct both the patient and nursing staff to record during the next 24 hours the volume or frequency and consistency of stool using visual Bristol Scale and also to provide a sample of stool. In case the patient has been discharged, he/she will be contacted the day before over the phone by a research nurse and the next day the patient will be asked to bring the formulary and a stool sample to hospital of will be visited by a research staff at home.

Afterwards, as long as the patient remains on ICU, adverse events, antibiotic treatment, and stool volume/frequency are monitored daily.

Unique Protocol ID: 2021-002290-25 22.9.2021 Protocol version 9.2

In patients with faecal management device in place, follow up visits (identical to Day 4) are performed in 7 days interval up to day 28, and/or ICU discharge or FMD removal, whichever occurs earlier.

In patients who remain in ICU, but have had FMD removed, have the same follow up procedures, with the exception of stool sampling. Stool is collected and stored as close as practical to the day of the visit after the patient has had spontaneously defecated.

In patients who are not on ICU, but remain at hospital, will be visited by a research nurse at day 7, 14, 21 and 28 as long as they remain hospitalised. The visit will include monitoring of adverse event, notice on patient general status, the presence/absence of diarrhoea, antibiotic medication. Blood will be collected and frozen. Six month follow up is performed at follow up clinics and it includes history (incl. recent history of diarrhoea), physical exam and blood sampling. Patients willing to do so are requested to bring in a stool sample. Patients unwilling to show up will be interviewed over the phone.

	D0	D1	D2	D3	D4	D 5-6	D7	D14, 21, 28or D/C	6month follow up
ICF	х								
Review drug chart	Х								
Serum sample + freeze	х	x			х		x	x	х
Stool sample + freeze	х				х		х	(x)	х
Adverse events, Phys.exam, SOFA	х	х	х	х	х	х	х	х	
Blood culture		хх							

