Primary outcome assessment							х		
in intervention group -FBT		х							

Unique Protocol ID: 2021-002290-25 22.9.2021 Protocol version 9.2

Table: Gantt diagram of study procedures. See text for details.

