# Monitoring of safety:

Although it is potentially beneficial and has been safely performed in ICU patients, there are only limited data about FBT safety in patients with potentially disrupted intestinal barrier. In turn, following measures have been taken to maximise safety of the current study for patients:

- Treating clinician will not be blinded to treatment allocation and they will be encouraged to speak up should any safety concerns arise.
- Before and 3 hours after FMT, vital signs, blood cultures, endotoxin and early cytokine levels will be measures to specifically look at potential bacterial translocation.
- All patients' vital functions will be continually monitored as per local standards. Frequency, volume and character (as per Bristol scale) of stools will be recorded in 12 hour intervals.
- Onset of sepsis or elevation lactate > 2mM or the presence of pyrexia >38 C with >30% rise of inflammatory markers without clear alternative reason (e.g. HAP) will trigger, in both groups, the addition of intravenous tigecycline or intravenous vancomycine, if C. dif positivity is known or suspected.
- I.v. antibiotics efficient against C. dif. can be added in both groups if a treating clinician considers this appropriate. Reason for doing so will be recorded.
- Should a SUSAR appear, it will be reported as per local legislature and within 48 hours reviewed by the team of investigators, together with independent safety advisors (prof. [name]. Dept. of Infectious Diseases, Na Bulovce Hospital, Prague and Dr.[name], REB Chair FNKV Univ. Hospital), a representative of nursing staff independent on the study. Two SUSARs in the intervention group would automatically lead to termination of the trial for safety reasons.

Unique Protocol ID: 2021-002290-25 22.9.2021 Protocol version 9.2

In addition, the same team will meet ad hoc whenever safety concerns arise. The
team will review data collected from first 8 subjects who have been randomised and
focus on the analysis of adverse events. In particular, the team will review the dynamics of body temperature, heart rate, blood pressure, lactate and blood cultures
before and after FMT. The decision will be taken to continue or terminate the study.

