# Statistical plan:

Safety parameters will be reported on intention-to-treat basis. Primary outcome will be compared by as unadjusted hazard ratio of not being cured (with 95% interval) in a per protocol analysis. The subset of patients with C. dif positivity will be analysed separately.

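### Two of the four named components of the safety composite cannot occur in a control patient, so an apparent FBT excess could be an artefact of the definition

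*Combined protocol and SAP*

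**What the plan says.** The section on secondary end-points defines a composite number of adverse events through an open list. New-onset sepsis and toxic megacolon come first, followed by "positive post FBT blood culture, or other SAE assessed by the physician-in-charge as possibly related to FBT".

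The blood culture is specified under the intervention group: "3hours after FBT blood culture will be taken". The section on monitoring of safety times it the same way: "Before and 3 hours after FMT, vital signs, blood cultures, endotoxin and early cytokine levels will be measures". The control-group section describes observation, with vancomycin for C. dif.-positive patients. It has no sham procedure and no matching culture time. In the schedule of procedures the FBT row is labelled "in intervention group -FBT". The Day 1 blood-culture row has no arm label, and the table refers the reader to the text. The row "Adverse events, Phys.exam, SOFA" carries no arm restriction.

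On blinding, the safety section states: "Treating clinician will not be blinded to treatment allocation". On analysis, the statistical plan says only: "Safety parameters will be reported on intention-to-treat basis". Safety is part of the aim in the abstract, and the sample-size section describes a pilot "with primary outcome being feasibility and safety of faecal bacterial transplantation".

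**The concern.** A between-arm count is interpretable only if the same event would be counted in either arm. Here two of the four named items depend on having received FBT. A contaminated or incidental positive culture three hours after the procedure counts in the FBT arm. The control arm has no procedure and no corresponding culture. A background SAE of a kind common in intensive care counts after FBT if the physician thinks a link possible, and that physician knows FBT was given. Under the fourth item, the same event in a control does not count.

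Safety is a stated purpose of the trial, and with 36 patients most readers will judge it from the by-arm table. If that table shows more events with FBT, the composite alone cannot show whether FBT caused harm or the definition produced the difference.

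**Working it through.** **Which items each arm can score, following the text as written**

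| Named component | FBT arm | Control treated as allocated |
|---|---|---|
| New-onset sepsis | yes | yes |
| Toxic megacolon | yes | yes |
| Positive post-FBT blood culture | yes | no: no FBT, no matching culture |
| Other SAE judged possibly related to FBT | yes | no: no FBT to relate it to |

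Two of four items have no control counterpart. C. dif.-positive patients in the intervention group have FBT repeated once, which may add a further culture opportunity in that arm only.

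**Inputs.** From the sample-size section: 36 patients randomised 1:1, so 36/2 = 18 per arm. The documents state no figure for the composite and no event rates, so there is no plan figure to reproduce. Every rate below is an assumption:

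- s = sepsis plus megacolon events per patient, equal in both arms (identical true harm)
- o = other SAEs per patient, equal in both arms
- q = share of other SAEs labelled possibly related to FBT
- c = incidental positive post-FBT cultures per patient

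**Formula.** Expected count per patient is s for control and s + q·o + c for FBT. Multiply by 18 for the arm total. The probability that FBT shows more events treats the two totals as independent Poisson counts.

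| Case (s = 0.20) | o | q | c | FBT per patient | FBT v control events | Ratio | P(FBT shows more) |
|---|---|---|---|---|---|---|---|
| Floor | any | 0 | 0 | 0.200 | 3.60 v 3.60 | 1.0 | 0.42 |
| Low | 0.20 | 0.05 | 0.02 | 0.20 + 0.01 + 0.02 = 0.230 | 4.14 v 3.60 | 1.15 | 0.50 |
| Middle | 0.30 | 0.25 | 0.05 | 0.20 + 0.075 + 0.05 = 0.325 | 5.85 v 3.60 | 1.63 | 0.72 |
| Worst | 0.40 | 1.00 | 0.10 | 0.20 + 0.40 + 0.10 = 0.700 | 12.60 v 3.60 | 3.5 | 0.99 |

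At the floor the comparison is symmetric: 0.42 more, 0.42 fewer, 0.15 tied.

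**Sensitivity to s.** With the middle-case inputs the FBT arm gains 0.075 + 0.05 = 0.125 events per patient, so the ratio is 1 + 0.125/s: 2.25 at s = 0.10, 1.63 at 0.20, 1.25 at 0.50 and 1.13 at 1.0. The ratio shrinks as the common event rate rises, but it never falls below 1.

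**Culture item alone.** The chance of at least one FBT-only event among 18 patients is 1 − (1 − c)^18: 0.30 at c = 0.02, 0.60 at 0.05 and 0.85 at 0.10.

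**A second model.** Counting patients with at least one event (binomial, 18 per arm), take a 10% common risk plus 5% incidental cultures and 5% FBT-attributed SAEs. The FBT risk is 1 − 0.90 × 0.95 × 0.95 = 18.8% against 10%. FBT shows more affected patients with probability 0.70, and control shows more with probability 0.16. The rates are again assumed, so this confirms the direction and does not estimate the size.

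**The case against.** The plan says safety will be reported. It reserves the language of comparison for the primary outcome, and no test, margin, stopping rule or sample size uses the composite. The SUSAR rule, the review of the first 8 patients and the SOFA endpoint do not depend on it. The distortion runs only against FBT, and closer surveillance of a new exposure in patients whose gut barrier may be impaired is deliberate. The culture before FBT gives a within-patient reference, and adverse events are recorded in both arms, so an unbiased count could be built later. The list is open-ended, and the unlabelled culture row leaves some doubt about whether controls are cultured. Finally, all the rates are assumed, and the illustration adds cultures to sepsis although one episode could be both.

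Much of this stands, and it limits the point to the by-arm summary and its interpretation. It does not remove the defect. Intention-to-treat reporting means display by randomised arm, which invites comparison. An open list may admit other control events, but it gives the two FBT-tied items no counterpart, and a control culture would still not follow FBT. The pre-FBT culture cannot exclude a contaminant that appears only at three hours. The both-arm records help only if the composite is redefined to use them. The uncertainty about rates affects the size of the bias; its direction follows from the definition.

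**Conclusion.** The concern holds. As defined, the composite can only be inflated in the FBT arm. With equal true harm its expected value is higher with FBT as soon as any incidental positive culture occurs or any background SAE is labelled as related. The size cannot be derived from the documents. In the assumed cases with s = 0.20 the ratio of expected counts runs from 1.0 to 3.5, and the middle case is sensitive to s (2.25 at 0.10, 1.13 at 1.0). These figures rest on independent Poisson counts, 18 patients per arm, treatment as allocated and no overlap between components.

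The consequence is limited: an FBT excess on this endpoint would be ambiguous, whereas no excess would remain reassuring. No planned inference is affected. The point should be corrected because safety is a stated aim and the correction is cheap.

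**What to change.** Keep a count of events for the by-arm safety summary, but build it only from components defined the same way in both arms: new-onset sepsis, toxic megacolon, and all SAEs whatever their judged relatedness. Count each event once, over one window for both arms (randomisation to day 28 or discharge, matching the adverse-event row of the schedule), and show each component separately beside the total.

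Report two items outside the composite, descriptively and for FBT recipients only: post-FBT blood cultures set against the pre-FBT culture, and SAEs judged possibly related to FBT. State in the schedule which arm the Day 1 blood-culture row covers.

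The cost is wording, since adverse events are already scheduled on the same days in both arms. There are two drawbacks. Unrelated intensive-care SAEs add noise at 18 per arm and could dilute an FBT-specific signal, which is why the components and the FBT-specific items are shown separately. Recording is also daily on ICU but weekly on the ward, so ascertainment is equal by schedule but could still differ if the arms leave ICU at different times. Reporting ICU days by arm would show whether that matters.

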## Informed consent procedure:

[figure not shown]
All patients with capacity will be asked to provide a prospective written informed consent (See Appendix 3). For patients without capacity, a deferred consent procedure will take a place. In this case, an independent clinician will review and sign that the patient is lacking capacity and he/she fulfils all criteria to be enrolled to the

Unique Protocol ID: 2021-002290-25 22.9.2021 Protocol version 9.2

study. The patient's next of kin will be informed about the study as soon as practical with the aid of information leaflet (Appendix 3). The patient will be asked to provide and sign informed consent as soon as he/she regains the capacity to do so. In case of consent refusal, patient's data will not be used in per-protocol analysis.

22.9.2021 Protocol version 9.2

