## Control group:

- we will wait for spontaneus retreat of diarrhea, which is a standard of care.
- in the subset of patients with C. dif. positivity, the patients receive 250 mg of vancomycine every 6 hour (with rescue option of conversion to i.v. tigecycline).

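### Two of the four named items in the only adverse-event end-point are defined by exposure to FBT, so the composite does not measure harm alike in the two arms

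*Combined protocol and SAP*

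**What the plan says.** The Secondary end-points section contains the only adverse-event outcome: a composite number of events, introduced by examples. Two examples, new-onset sepsis and toxic megacolon, make no reference to treatment. The other two are "positive post FBT blood culture, or other SAE assessed by the physician-in-charge as possibly related to FBT".

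Other sections bear on how these items work:

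- **Control group:** "we will wait for spontaneus retreat of diarrhea, which is a standard of care", with vancomycin if C. dif. is positive. No FBT, sham enema or crossover is described.
- **Intervention group:** "3hours after FBT blood culture will be taken".
- **Monitoring of safety:** "Before and 3 hours after FMT, vital signs, blood cultures, endotoxin and early cytokine levels will be measures". The same section states "Treating clinician will not be blinded to treatment allocation".
- **Statistical plan:** "Safety parameters will be reported on intention-to-treat basis". The parameters are not listed and no between-arm estimate is specified for them.
- **Visit text for days 2 and 3, and the schedule table under Assessment of primary outcome:** adverse events are recorded with no restriction by arm.

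No primary, secondary or exploratory outcome is all-cause death or all SAEs.

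**The concern.** A safety outcome in a randomised trial is informative when the same event in either arm is counted in the same way. Here, half of the named items need an FBT to have taken place. A serious event in a control that is neither sepsis nor toxic megacolon has no named item to fall under. The same event in the FBT arm counts or not according to an attribution made by a clinician who knows the allocation.

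Safety is a stated aim in the Abstract and in the sample-size section, and the safety section concedes that data on FBT are limited where the gut barrier may be disrupted. Read across arms, the composite could show an excess with FBT when total harm is equal. It could also leave out serious events in the FBT arm that are put down to the underlying illness, or miss a reduction in serious events relative to control. Analysing by intention to treat fixes who is in the denominator. It does not repair an event definition that is empty in one arm.

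**Working it through.** **1. The plan's own figure.** The sample-size section gives 36 patients, 1:1, from success rates of 45% and 66%, a 20-point margin, one-sided alpha 0.05 and 80% power. With unpooled variance, n per arm = (0.45×0.55 + 0.66×0.34) × (1.645 + 0.842)² / (0.21 + 0.20)² = 0.4719 × 6.185 / 0.1681 = 17.36, rounded up to 18, or 36 in total. The figure reproduces and is not in dispute. It is used here only for n = 18 per arm.

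**2. The four named items, arm by arm.**

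| Named item | Can count with FBT | Can count in controls, as worded |
|---|---|---|
| New-onset sepsis | yes | yes |
| Toxic megacolon | yes | yes |
| Positive blood culture after FBT | yes | no |
| Other SAE possibly related to FBT | yes, if so judged | no |

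The text ties the culture to FBT twice (Intervention group; Monitoring of safety). The schedule table marks blood culture on day 1 without naming an arm, although its FBT row does name the intervention group. Control cultures on day 1 therefore cannot be ruled out, but the end-point would still count only a culture taken after FBT.

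**3. What this does to a comparison, taking the named list as complete.** Let k_T and k_C be the SAEs other than sepsis or toxic megacolon in the FBT and control arms. Let r be the number of k_T judged possibly related (0 ≤ r ≤ k_T), and b the positive post-FBT cultures not already counted as another event.

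- The two FBT-tied items contribute b + r with FBT and 0 in controls.
- A count that ignores attribution would give k_T and k_C.
- Distortion of the difference: D = (b + r) − (k_T − k_C) = b + k_C − (k_T − r).

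D is positive (against FBT) when b + k_C exceeds the number of FBT-arm SAEs judged unrelated. It is negative (in favour of FBT) when it falls short. The documents fix none of these quantities, so the sign is not determined.

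Three made-up cases with b = 0 show the mechanism only:

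- k_T = 3, k_C = 3: appears as 0–3 v 0; D = r, from 0 to 3.
- k_T = 2, k_C = 5: appears as 0–2 v 0, although the controls had three more; D = 3 + r, from 3 to 5.
- k_T = 5, k_C = 2, none judged related: appears as 0 v 0; D = 2 − 5 = −3.

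**4. Precision of the arm-neutral count.** Exact (Clopper–Pearson) 95% intervals for patients with an event out of 18: 0/18, 0 to 18.5% (upper limit 1 − 0.025^(1/18)); 2/18, 1.4 to 34.7%; 5/18, 9.7 to 53.5%. Such counts describe; they do not test.

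**The case against.** The strongest reply has four parts.

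**No between-arm comparison is stated.** The statistical plan says that the primary outcome is compared but that safety is reported. A reader might infer that a formal between-arm test of the composite is planned; the documents do not say so. Setting the arms side by side is the natural use of a secondary end-point in a randomised trial, but it is an inference, and the point is conditional on it.

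**The list is open.** The four items are examples, so a control SAE might be counted after all. This stands: the zero in controls follows from the wording of the two items, not from the composite under every reading. But no rule says what else counts, and the choice could then be made by people who know the allocation.

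**Harm is tracked in both arms.** Adverse events are recorded throughout, SOFA is a secondary end-point at days 4 and 7, and sepsis counts alike. A reader might infer from the absence of a mortality or all-SAE outcome that deaths or control-arm events go unrecorded. The recording provisions do not support that. What remains is that SOFA counts neither deaths nor SAEs, and no outcome requires either to be shown by arm.

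**Procedure-specific items have a purpose.** Cultures around the procedure look for translocation, and the safety advisors review them in the first 8 randomised patients. In an open-label enema trial an unblinded treating physician is hard to avoid. This is a good reason to keep the items, but within the FBT arm and not in a composite read across arms.

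**Conclusion.** The point holds in a limited form. Two of the four named items depend on FBT exposure, and one of those also depends on an unblinded judgement of relatedness. A side-by-side reading of the composite therefore does not measure harm alike. This is a fault in the end-point's definition, not in the capture of events.

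Its size cannot be given, because the documents contain no SAE or mortality rates and the cases shown are invented. A reader might infer a bias against FBT, since the extra items can count only there. The wording does not establish that: the relatedness filter can also remove FBT-arm events, and the net direction is uncertain.

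The conclusion assumes that the composite will be shown by arm, and that the two items are applied as written. It should be corrected, because safety is a stated aim and the change is cheap. It does not affect the sample size or the primary outcome.

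**What to change.** Amend the Secondary end-points and Statistical plan sections as follows.

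1. Limit the between-arm safety end-point to arm-neutral events: new-onset sepsis, toxic megacolon, all SAEs regardless of judged relatedness, and all-cause deaths. Count to hospital discharge or day 28, whichever is earlier, the horizon already used for recurrence.
2. Report these descriptively by randomised arm: number of events, and number of patients with at least one, with exact 95% confidence intervals.
3. Report blood cultures before and after FBT, and the judgement of FBT-relatedness, within the FBT arm only.
4. Optionally add deaths known at the 6-month contact, with the number of patients of unknown status by arm.

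The cost is protocol wording and one table. No visit or patient is added, because adverse events are already recorded to day 28 or discharge. The downsides are wide intervals with 18 per arm and some missing vital status after discharge: no day-28 contact is scheduled for discharged patients, and the 6-month contact is with the patient.

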# Primary end-point:

• Percentage of patients with treatment failure at day 7 after randomisation. Treatment failure is defined as either failure to administer allocated treatment for any reason or the presence of diarrhoea on day 7 after randomisation (as assessed by personnel blinded to treatment allocation).

22.9.2021 Protocol version 9.2

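### Recurrence-free status is read at the earlier of discharge and day 28, so patients are watched for different lengths of time, and neither recurrence nor the denominator is defined

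*Combined protocol and SAP*

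**What the plan says.** The protocol's section on secondary end-points lists the "Percentage of patients that are recurrence-free at time of hospital discharge or day 28, whichever occur earlier". It does not define recurrence, does not require that diarrhoea first resolved, and does not say who is in the denominator or how deaths are classed.

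For patients who have left the ICU, the section on assessment of the primary outcome says they "will be visited by a research nurse at day 7, 14, 21 and 28 as long as they remain hospitalised". The schedule table heads the same column with days 14, 21, 28 or discharge. After discharge, two contacts are described:

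- **Day 7:** "In case the patient has been discharged, he/she will be contacted the day before over the phone by a research nurse". The patient then brings a form and stool sample to hospital or is visited at home.
- **Six months:** "Six month follow up is performed at follow up clinics and it includes history (incl. recent history of diarrhoea), physical exam and blood sampling", with the allowance that "Patients unwilling to show up will be interviewed over the phone". This visit is not linked to the recurrence endpoint.

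The primary endpoint does classify uncured patients: "Treatment failure is defined as either failure to administer allocated treatment for any reason or the presence of diarrhoea on day 7 after randomisation". That rule is not carried over to the recurrence endpoint. The statistical plan covers safety, the primary outcome and the C. dif. subset. It gives no analysis for recurrence and no method for unequal follow-up.

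**The concern.** Leaving hospital is a post-randomisation event, and here it ends the observation window. A patient discharged on day 10 has about 3 days after the day-7 assessment in which a recurrence could be recorded; one who stays to day 28 has 21. For a patient discharged before day 7, the endpoint closes before cure has been assessed at all. The protocol foresees such patients, since it plans a day-7 contact for them.

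The Background section says that postantibiotic diarrhoea often lengthens the stay, and treating clinicians know the allocation. Discharge timing may therefore differ by arm. Even if it does not, the reported percentage mixes windows of different lengths and cannot be read as a 28-day recurrence result.

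Separately, the missing definition leaves open whether a patient whose diarrhoea never stopped counts as recurrence-free. Different answers give different comparisons between the arms, so the choice should be made before data are seen. This is the only listed endpoint that addresses how durable a cure is.

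**Working it through.** **The plan's own figure.** The recurrence endpoint has no planning figure. The sample size section gives 36 patients from cure rates of 45% and 66%, a margin of 20 points, one-sided 5% and 80% power:

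n per arm = (1.645 + 0.842)² × (0.45 × 0.55 + 0.66 × 0.34) / (0.21 + 0.20)² = 6.18 × 0.4719 / 0.1681 = 17.4, rounded up to 18, or 36 in total. This reproduces, and nothing below changes it.

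**Step 1: unequal windows.** Inputs: the endpoint's reading time (from the protocol); recurrence risk r over days 7 to 28 and a constant hazard (both assumed).

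Hazard h = −ln(1 − r)/21 per day. Recurrence observed by discharge day d = 1 − exp(−h(d − 7)).

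With r = 25%, h = 0.2877/21 = 0.0137:

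- Discharge on day 12: 1 − exp(−5 × 0.0137) = 6.6%
- Discharge on day 18: 1 − exp(−11 × 0.0137) = 14.0%
- Still in hospital on day 28: 25%

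The same underlying risk gives a 7.4-point gap between discharge on day 12 and on day 18. With r = 20%, the proportion seen as recurrence-free is 96.9% for discharge on day 10, 92.8% on day 14, 86.2% on day 21 and 80.0% at day 28. For r from 10 to 30%, it runs from 98.5 to 95.0% at day 10 and from 90.0 to 70.0% at day 28.

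These figures show how strongly the window drives the result. They do not estimate a difference between arms.

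**Step 2: the undefined denominator.** Inputs: cure rates c of 66% for FBT and 45% for control (sample size section); recurrence risk r among the cured, assumed equal in both arms and observed in full to day 28.

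| Rule | Formula | FBT, r = 25% | Control, r = 25% |
|---|---|---|---|
| Never-cured count as recurrence-free | 1 − c × r | 83.5% | 88.8% |
| Cured patients only | 1 − r | 75% | 75% |
| Never-cured count as failures | c × (1 − r) | 49.5% | 33.8% |

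Under the first rule the gap is (0.66 − 0.45) × r = 0.21 × r in favour of control: 3.2 points at r = 15%, 5.3 at 25% and 7.4 at 35%. The second rule shows no difference. The third favours FBT by 0.21 × 0.75 = 15.8 points. The documents do not say which rule applies.

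**Step 3: both effects together.** Take the first rule, r = 25%, every FBT patient discharged on day 12 and every control patient on day 18 (assumed):

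- FBT: 1 − 0.66 × 0.066 = 95.6%
- Control: 1 − 0.45 × 0.140 = 93.7%

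FBT is now ahead by about 2 points (1.2 to 2.7 for r from 15 to 35%). The two effects can oppose each other, so the net direction cannot be derived from the documents.

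**The case against.** A reader might infer that the endpoint as written counts never-cured patients as successes and so makes the better arm look about 5 points worse. The documents do not support that. The text says patients without restriction, but recurrence ordinarily presupposes resolution, so a cured-only denominator is an equally natural reading and shows no reversal. Step 3 shows that the reversal also disappears under one plausible pattern of discharge. Counting never-cured patients as successes is possible, not prescribed.

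A reader might also infer that the arm with more cures must be discharged earlier and so be flattered. That goes too far as well. The Background section suggests that ongoing diarrhoea prolongs stay, which mainly concerns uncured patients, who have nothing to recur from. It gives no direct reason why cured patients in one arm should leave earlier than cured patients in the other. Patients are enrolled from ICU or HDU with an expected stay beyond 7 days and the endpoint uses hospital discharge, so very early discharges may be uncommon.

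Finally, this is one secondary endpoint of a feasibility trial, with no test specified. Of 18 patients per arm, 5 points is about one patient (0.0525 × 18 = 0.9), and non-cure is already visible in the primary endpoint.

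These arguments limit the size and the certainty. They do not remove the rule that closes observation at discharge, or the absence of a definition.

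**Conclusion.** The point holds in two parts. First, the stated reading time gives patients unequal observation windows that depend on a post-randomisation event, and no analysis is planned to deal with this. That follows from the text and needs no assumption. The 6.6% and 14.0% illustration rests on an assumed 25% risk, a constant hazard and assumed discharge days; the size and direction of any net bias between arms are unknown.

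Second, recurrence and its denominator are undefined, and the choice can move the comparison from 3 to 7 points in favour of the arm with fewer cures, through no difference, to a clear advantage for the arm with more cures. This rests on the planning cure rates, which come from non-critically ill patients with C. dif., and on equal recurrence risk in both arms.

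It is a cheap improvement to a secondary endpoint. The sample size and primary analysis are unaffected.

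**What to change.** Replace the endpoint with sustained resolution at a fixed day 28 in all randomised patients:

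- Diarrhoea has resolved by day 7 under the protocol's own definition and has not returned by day 28.
- Patients whose diarrhoea has not resolved by day 7 count as not achieving it. Later resolution can be described separately.
- Deaths before day 28 are classified by a stated rule and also reported separately.
- For discharged patients, a research nurse obtains day-28 status by telephone interview. The precedent is the six-month telephone interview; the day-7 call only arranges an assessment.
- Patients who cannot be reached are reported, with a best-case and worst-case sensitivity analysis.

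Time to recurrence censored at discharge should not be the main alternative: discharge may be related to diarrhoea, so the censoring may be informative, and restricting to cured patients gives up the randomised comparison.

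The cost is at most 36 short calls, some missing answers, and telephone recall that is less precise than in-hospital stool records. Because recall would be used only after discharge, the source of each day-28 status should be reported by arm.
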